### **16.3. DEFINITIONS AND FOLLOW-UP REQUIREMENTS**

Definition of ineligible patients: A study participant who is registered to the study but does not meet all of the eligibility criteria is deemed to be ineligible.

Definition of clinical follow-up: The follow-up period where the study participant is no longer receiving treatment, but is still following the study calendar for tests, exams, and correlative endpoints (e.g., specimen collection, quality of life, disease assessments as required by the study).

Definition of survival only follow-up: The follow-up period where the study participant is monitored for long-term endpoints, is no longer receiving study treatment, and is not required to follow the study calendar for tests, exams, and correlative endpoints (e.g. specimen collection, quality of life, disease assessments as required by the study). In this follow-up period, there is a schedule in which case

report forms should be submitted, but the physician visits are based on the standard of care.

#### **16.4. FOLLOW UP FOR INELIGIBLE PATIENTS**

Study participants who are registered to the study and receive any protocol treatment but deemed ineligible must follow the schedule of assessments detailed in Section 9.

#### **16.5. FOLLOW-UP FOR PATIENTS NEVER RECEIVING PROTOCOL INTERVENTION**

Study participants who are enrolled into the study but who never go on to receive study intervention must still complete follow-up requirements as specified below.

Screening, on-study, endpoint (e.g., relapse or progression), and survival data submission required.

### **17. ADVERSE EVENTS**

An adverse event (AE) is defined as any untoward medical occurrence in a patient or clinical investigation subject administered a pharmaceutical product and which does not necessarily have to have a causal relationship with this treatment. An adverse event can therefore be any unfavorable and unintended sign (including an abnormal laboratory finding, for example), symptom, or disease temporally associated with the use of a medicinal product or protocol-specified procedure, whether or not considered related to the medicinal product or protocol-specified procedure. Any worsening (i.e., any clinically significant adverse change in frequency and/or intensity) of a preexisting condition that is temporally associated with the use of pembrolizumab is also an adverse event.

Changes resulting from normal growth and development that do not vary significantly in frequency or severity from expected levels are not to be considered adverse events. Examples of this may include, but are not limited to onset of menses or menopause occurring at a physiologically appropriate time.

Adverse events may occur during the course of the use of pembrolizumab (or topotecan) during this study, or as prescribed in clinical practice, from overdose (whether accidental or intentional), from abuse and from withdrawal.

Progression of small cell lung cancer is not considered an adverse event unless it is considered to be drug related by the investigator.

The prompt reporting of adverse events is the responsibility of each investigator engaged in clinical research, as required by Federal Regulations. Adverse events must be described and graded using the terminology and grading categories defined in the NCI's Common Terminology Criteria for Adverse Events (CTCAE), Version 4.0. The CTCAE is available at [ctep.cancer.gov/protocolDevelopment/electronic\\_applications/ctc.htm](http://ctep.cancer.gov/protocolDevelopment/electronic_applications/ctc.htm). Attribution to protocol treatment for each adverse event must be determined by the investigator and reported on the required forms, using the codes provided.

## 17.1. ROUTINE ADVERSE EVENT REPORTING

Adverse event data collection and reporting, which are required as part of every clinical study are done to ensure the safety of patients enrolled in the studies as well as those who will enroll in future studies using similar agents. AEs will be recorded as part of medical history during Screening. All adverse events that occur after the consent form is signed but before treatment allocation/randomization must be reported by the investigator if they cause the subject to be excluded from the study, or are the result of a protocol specified intervention, including but not limited to washout or discontinuation of usual therapy, diet, placebo treatment or a procedure. Any new AEs or increase of a documented AE from screening/history will be recorded from the time of the first treatment allocation/randomization through 30 days following cessation of treatment. Adverse events are reported in a routine manner at scheduled times according to the study calendar in Section 9. All adverse events are entered into the eCRF in Rave. The investigator will make every attempt to follow all subjects with non-serious adverse events for outcome.

Adverse events will not be collected for patients during the pre-screening period as long as that patient has not undergone any protocol-specified procedure or intervention. If the patient requires a blood draw, fresh tumor biopsy etc., the patient is first required to provide consent to the main study and AEs will be captured according to guidelines for standard AE reporting.

## 17.2. EXPEDITED ADVERSE EVENT REPORTING

Investigators are required by Federal Regulations to report serious adverse events as defined in the table below. Investigators are required to notify the AFT and their Institutional Review Board if a patient has a reportable serious adverse event. **The descriptions and grading scales found in the NCI Common Terminology Criteria for Adverse Events (CTCAE) version 4 will be utilized for AE reporting.** The CTCAE is identified and located on the CTEP website at: [ctep.cancer.gov/protocolDevelopment/electronic\\_applications/ctc.htm](http://ctep.cancer.gov/protocolDevelopment/electronic_applications/ctc.htm). All SAEs/Infusion Associated Reactions (IARs) must be entered into the eCRF via Rave EDC within 24 hours of learning of the event. This will allow the safety monitor and monitor to review the information and assess the safety of the patient.

**Note: All deaths on study require reporting via Rave EDC, regardless of causality. Attribution to treatment or other cause should be provided.**

### 17.2.1. Serious Adverse Event (SAE)

For the time period beginning when the consent form is signed until treatment allocation/randomization, any serious adverse event, or follow up to a serious adverse event due to any cause other than progression of the cancer under study that occurs to any subject must be reported within the timelines listed in Table 12 below if it causes the patient to be excluded from the study, or is the result of a protocol-specified intervention, including but not limited to washout or discontinuation of usual therapy, diet, placebo treatment or a procedure.

**Table 12. Serious Adverse Event Reporting Requirements**

REPORTING REQUIREMENTS FOR SERIOUS ADVERSE EVENTS				

NOTE: Investigators MUST immediately report to the sponsor (AFT) ANY Serious Adverse Events, whether or not they are considered related to the investigational agent(s)/intervention (21 CFR 312.64)
 
An adverse event is considered serious if it results in ANY of the following outcomes:
 
 
1) Death
 
2) A life-threatening adverse event
 
3) An adverse event that results in inpatient hospitalization or prolongation of existing hospitalization for ≥ 24 hours
 
4) A persistent or significant incapacity or substantial disruption of the ability to conduct normal life functions
 
5) A congenital anomaly/birth defect
 
 
Note: Important Medical Events (IME) that may not result in death, be life threatening, or require hospitalization may be considered serious when, based upon medical judgment, they may jeopardize the patient or patient and may require medical or surgical intervention to prevent one of the outcomes listed in this definition. In addition to the above criteria, although not serious per ICF definition, are reportable to AFT in the same timeframe as SAEs to meet certain local requirements. Therefore these events are considered serious by AFT for collection purposes:
 
 
• The development of a new cancer (that is not a condition of the study)
 
• Is associated with an overdose
 
				

ALL SERIOUS adverse events that meet the above criteria MUST be immediately reported to the AFT via the Rave Electronic Data Capture (EDC) system within the timeframes detailed in the table below. AFT will send SAE reports to Merck Global Safety within 2 working days.
				
Hospitalization	Grade 1 Timeframes	Grade 2 Timeframes	Grade 3 Timeframes	Grade 4 & 5 Timeframes
Resulting in Hospitalization > 24 hrs	Enter into Rave EDC within 24 hours of the sites awareness of the event			
Not resulting in Hospitalization ≥ 24 hrs	Not required to enter into Rave EDC as an SAE.		Enter into Rave EDC as an SAE within 24 hours of the sites awareness of the event	

Expedited AE reporting timelines are defined as:
 
 
• “All Grade 3, 4 and 5 AEs: 24-Hour; 4 Calendar Days” - The AE must initially be reported via Rave EDC ≤ 24 hours of learning of the AE, followed by a complete expedited report ≤ 4 calendar days of the initial 24-hour report.
 
• “All Grade 1 and 2 AEs resulting in hospitalization or prolonged hospitalization: 24-Hour; 10 Calendar Days” - The AE must initially be reported via Rave EDC ≤ 24 hours of learning of the AE, followed by a complete expedited report ≤ 10 calendar days of the initial 24-hour report.
 
				

Serious adverse events will be recorded from the time of treatment allocation/randomization through 90 days following cessation of treatment, or 30 days following cessation of treatment if the patient initiates a new antineoplastic therapy, whichever comes first. Any serious adverse event, or follow up to a serious adverse event, including death due to any cause other than progression of the cancer under study whether or not related to pembrolizumab (MK-3475) must be reported into Rave EDC within 24 hours of awareness of the event.

Additionally, any serious adverse event, considered by an investigator who is a qualified physician to be related to pembrolizumab (MK-3475) that is brought to the attention of the investigator at any time following consent through the end of the specified safety follow-up period specified in the paragraph above, or at any time outside of the time period specified in the previous paragraph must also be reported immediately to AFT.

All patients with serious adverse events must be followed up for outcome.

**NOTE:** Deaths occurring outside of the serious adverse event reporting period that are clearly due to progressive disease should be reported via routine reporting methods in the Rave data capture system. Deaths occurring within the reporting window, even if considered to be related to disease progression as the cause of death should be reported within Rave EDC with death noted as the outcome of the event.

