### **17.3. EVALUATING ADVERSE EVENTS**

An investigator who is a qualified physician will evaluate all adverse events according to the NCI Common Terminology for Adverse Events (CTCAE), version 4.0. Any adverse event which changes CTCAE grade over the course of a given episode will have each change of grade recorded on the adverse event case report forms/worksheets.

All adverse events regardless of CTCAE grade must also be evaluated for seriousness. See Table 13 below for additional guidance.

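### Table 12 exempts Grade 1–2 events without hospitalization from SAE entry even when they meet its outcome-based definition of serious, and its Grade 3–5 timeline lacks a seriousness qualifier

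*Combined protocol and SAP*

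**What the plan says.** Section 17.2.1, Table 12 has four parts that bear on this point.

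- **Definition.** An event is serious by its outcome: death, threat to life, hospitalization, congenital anomaly, or "A persistent or significant incapacity or substantial disruption of the ability to conduct normal life functions". Important medical events are added by medical judgment. New cancers and overdose-associated events are added too: "Therefore these events are considered serious by AFT for collection purposes". No grade appears. The table's opening note tells investigators to report any serious event immediately, whether or not it is thought related.
- **Lead-in to the grid.** It refers to serious "adverse events that meet the above criteria" and sends the reader to the timeframes below.
- **Grid.** For events without hospitalization of at least 24 hours, the lower grades carry "Not required to enter into Rave EDC as an SAE" and the higher grades carry "Enter into Rave EDC as an SAE within 24 hours of the sites awareness of the event".
- **Timelines.** One line reads "All Grade 3, 4 and 5 AEs: 24-Hour; 4 Calendar Days". The other reads "All Grade 1 and 2 AEs resulting in hospitalization or prolonged hospitalization: 24-Hour; 10 Calendar Days".

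Elsewhere, Section 17.3 says "All adverse events regardless of CTCAE grade must also be evaluated for seriousness". Section 17.2 and the text after Table 12 require SAEs to be entered within 24 hours, with no grade limit. Section 17.2.4 makes an adverse event resulting from a pembrolizumab overdose an SAE even where no other criterion is met.

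**The concern.** The definition asks what happened to the patient. The grid asks what grade the event was and whether the patient was admitted. The two tests give different answers for some events, and a site has to choose one.

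At the lower grades the risk is under-reporting: an event judged serious need not be entered as an SAE, so the 24-hour clock and the onward report to the drug supplier within 2 working days may not start. At the higher grades the risk is over-reporting: a site that takes the timeline literally enters events that meet no seriousness criterion. Either way, an SAE listing or table would mix events classified by different rules at different sites. Safety and tolerability of pembrolizumab is a secondary objective (Section 6.2).

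**Working it through.** There is no stated figure to reproduce. The check sets the passages side by side and asks how each kind of event is handled.

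**Step 1: where the grid splits.** In the available text the no-hospitalization row shows two entries across four grade columns, so the cells are evidently merged. The timelines divide at the same place, Grade 1–2 on one side and Grade 3–5 on the other. I therefore read the exemption as covering Grade 1–2 and the entry rule as covering Grade 3 and above.

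**Step 2: compare the readings for events without hospitalization.**

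| Event | Outcome definition | Grid limited to serious events (lead-in governs) | Grid and timeline taken literally |
|---|---|---|---|
| Grade 1–2, serious by another criterion (important medical event, incapacity, new cancer, overdose-associated) | SAE, report | Exempt from SAE entry | Exempt from SAE entry |
| Grade 3, or asymptomatic Grade 4, meeting no criterion | Not an SAE | Outside the grid | Entered as an SAE |
| Grade 5 | SAE | Entered | Entered |

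In the first row the grid contradicts the definition under both readings. In the second it does so only under the literal reading. In the third there is no conflict.

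**Step 3: Grade 4.** Table 13 describes Grade 4 in terms of life-threatening consequences, which overlaps the outcome criterion. The same table restricts the seriousness criterion to immediate risk of death from the event as it actually occurred. A Grade 4 laboratory value without symptoms need not meet that, so the second row is not confined to Grade 3.

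**Step 4: does routine AE collection fill the Grade 1–2 gap?** Section 17.1 puts all adverse events into the eCRF, so the event is not lost while routine collection runs. That collection ends 30 days after treatment stops. SAE collection runs to 90 days unless new anticancer therapy begins. Between those points, a serious Grade 1–2 event exempted from SAE entry has no routine route in, unless it is also an event of clinical interest.

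**Step 5: does SAE status enter a specified analysis or rule?** Section 20 summarizes treatment-related toxicity by grade, type and system organ class, and compares the percentages of subjects with an adverse event by Fisher's exact test. Section 19.3 suspends accrual on related Grade 4/5 non-hematologic events and on treatment-related deaths. Neither uses SAE status.

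**The case against.** **The lead-in limits the grid.** Table 12 is titled for serious events, its columns are labelled as timeframes, and the lead-in confines it to events meeting the criteria. This stands for the upper grades: a careful site would use the Grade 3–5 line only for timing. It does not help the lower grades. If the grid holds only serious events, the Grade 1–2 cell exempts events that are, by that premise, serious.

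**Other sections require reporting anyway.** Sections 17.2, 17.2.1 and 17.2.4 do so. They show what was probably intended, but they form one side of the contradiction and do not tell a site which text prevails. The affected set is probably small.

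**Wider expedited collection may be deliberate.** A sponsor may want prompt notice of all Grade 3–4 events. That is a legitimate choice, but the grid says to enter them as SAEs, which merges a collection preference with a classification.

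**Two stronger readings are tempting, and the documents support neither.**

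- A reader might infer that the plan turns every Grade 3–5 event into an SAE. That is one literal reading of an unqualified line, against the lead-in. Grade 5 is serious in any case.
- A reader might infer that SAE counts would rise mainly on topotecan and make pembrolizumab look safer. Section 4.2.2 does cite Grade 4 neutropenia in 7% and Grade 4 thrombocytopenia in 5% of courses. Those figures cover all such events, not those whose SAE status changes between readings. The documents give no serious/non-serious split and no pembrolizumab Grade 3–4 rate. Let T and P be the proportions of topotecan and pembrolizumab patients reclassified. With 31 and 62 patients, the topotecan count rises more only if 31T > 62P, that is T > 2P. Taking T = 30% purely as an assumption gives 31 × 0.30 = 9.3 patients. Against this, P = 10% gives 62 × 0.10 = 6.2, and P = 20% gives 62 × 0.20 = 12.4. The direction in counts reverses within a plausible range. As a percentage of the arm, topotecan shifts more only if T > P, which is equally unknown.

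**Conclusion.** The point holds as a contradiction in safety-reporting text. The Grade 1–2 conflict is firm: it survives either reading of the grid and rests only on the Grade 2/3 split, which the timelines support. The Grade 3–5 problem is an ambiguity, real only at sites that follow the timeline and grid over the lead-in.

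The size cannot be estimated. The documents give no frequency for serious Grade 1–2 events without hospitalization, nor for non-serious Grade 3 or asymptomatic Grade 4 events in either arm. No claim about a difference between arms is justified. The consequence is limited to SAE entry, onward safety reporting and any SAE tabulation. The primary analysis, the specified adverse-event comparison and the suspension rule are unaffected.

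**What to change.** - State in Section 17.2.1 that the outcome-based definition alone decides whether an event is entered as an SAE, and that grade and hospitalization set only the reporting timeline.
- Change the Grade 1–2 cell so that any event meeting a seriousness criterion is entered within 24 hours, and extend the Grade 1–2 timeline, now confined to hospitalized events, to match.
- Insert the word serious into the Grade 3–5 timeline line. If wider expedited collection is intended, label those additional events as expedited but not SAEs, so that they can be kept apart in any table.
- In the same edit, reconcile the length-of-stay wording. The Table 12 definition uses at least 24 hours, one grid row uses more than 24 hours, and Table 13 counts any inpatient admission. This is a separate mismatch in the same text.

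The cost is amendment wording and a short note to sites. If sites have been entering non-serious Grade 3–4 events as SAEs, expedited reports may fall. If SAEs have already been entered, one pass over the Grade 1–2 events judged serious and over the Grade 3–4 SAEs would put them on a single definition. No treatment rule, sample size or specified analysis changes.

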#### **17.2.2. Events of Clinical Interest and Immune Related Adverse Events**

Selected non-serious and serious adverse events are also known as (ECI) and/or Immune Related Adverse Events (irAEs) and must be reported within 24 hours within Rave EDC system.

For the time period beginning when the consent form is signed until treatment allocation/randomization, any ECI, or follow up to an ECI, that occurs to any subject if it causes the subject to be excluded from the study, or is the result of a protocol-specified intervention, including but not limited to washout or discontinuation of usual therapy, diet, placebo treatment or a procedure must be reported as an SAE within Rave EDC within System 24 hours and AFT will report to Merck Global Safety within 2 days

For the time period beginning at treatment allocation/randomization through 90 days following cessation of treatment, or 30 days following cessation of treatment if the subject initiates new anticancer therapy, whichever is earlier, any ECI, or follow up to an ECI, whether or not related to pembrolizumab (MK-3475), must be reported within via Rave EDC within 24 hours and AFT will report to Merck Global Safety within 2 days

ECIs/ir AEs for this study include:

1. An overdose of pembrolizumab, as defined in Section 16.3 - Definition of an Overdose for This Protocol and Reporting of Overdose to AFT, that is not associated with clinical symptoms or abnormal laboratory results.
2. An elevated AST or ALT lab value that is greater than or equal to 3X the upper limit of normal and an elevated total bilirubin lab value that is greater than or

equal to 2X the upper limit of normal and, at the same time, an alkaline phosphatase lab value that is less than 2X the upper limit of normal, as determined by way of protocol-specified laboratory testing or unscheduled laboratory testing.\*

\*Note: These criteria are based upon available regulatory guidance documents. The purpose of the criteria is to specify a threshold of abnormal hepatic tests that may require an additional evaluation for an underlying etiology.

### **17.2.3. Protocol-Specific Exceptions to Serious Adverse Event Reporting**

Efficacy endpoints as outlined in this section will not be reported to AFT as described in Section 16.2.1 – Table 12, unless there is evidence suggesting a causal relationship between pembrolizumab and the event. Any such event will be submitted to AFT via Rave EDC within 24 hours and AFT will report to Merck Global safety within 2 working days.

Specifically, the suspected/actual events covered in this exception include any event that is disease progression of the cancer under study.

AFT will monitor unblinded aggregated efficacy endpoint events and safety data to ensure the safety of the subjects in the study. Any suspected endpoint which upon review is not progression of the cancer under study will be forwarded by AFT to Merck Global Safety within 2 working days of determination that the event is not progression of the cancer under study.

Hospitalization related to convenience (e.g. transportation issues etc.) will not be considered a SAE.

### **17.2.4. Definition of an overdose for this protocol and reporting of overdose to AFT**

For purposes of this study, an overdose will be defined as any dose exceeding the prescribed dose for pembrolizumab by 20% over the prescribed dose. No specific information is available on the treatment of overdose of pembrolizumab. In the event of overdose, pembrolizumab should be discontinued and the patient should be observed closely for signs of toxicity. Appropriate supportive treatment should be provided if clinically indicated.

If an adverse event(s) is associated with (“results from”) the overdose of a pembrolizumab, the adverse event(s) is reported as a serious adverse event, even if no other seriousness criteria are met.

If a dose of pembrolizumab meeting the protocol definition of overdose is taken without any associated clinical symptoms or abnormal laboratory results, the overdose is reported as a non-serious Event of Clinical Interest (ECI), using the terminology “accidental or intentional overdose without adverse effect.”

